Study Protocol

Protocol Number: MT-8554-A02

An open-label, long-term extension study of MT-8554 in postmenopausal women
experiencing moderate to severe vasomotor symptoms who completed
Study MT-8554-A01

Protocol Version: Final incorporating Amendment 5
Protocol Amendment Date: 13 August 2019

NCT number: NCT03541200

Protocol Number: MT-8554-A02

**An open-label, long-term extension study of MT-8554 in postmenopausal women
experiencing moderate to severe vasomotor symptoms who completed
Study MT-8554-A01**

IND Number: [REDACTED]

EudraCT Number:

Investigational Medicinal Product: MT-8554

Indication: Treatment of moderate to severe vasomotor symptoms (VMS) associated with menopause

Sponsor: Mitsubishi Tanabe Pharma Development America, Inc.
[name]

Protocol Version: Final incorporating Amendment 5

Protocol Date: 13 August 2019

Strictly Confidential Information

Mitsubishi Tanabe Pharma Corporation, Mitsubishi Tanabe Pharma Development America, Inc., their successors and/or assignees are collectively referred to as Mitsubishi. The information contained in this protocol is the property of Mitsubishi. This information is confidential and is to be used only in connection with matters authorized by Mitsubishi and no part of it is to be disclosed to others without prior written permission from Mitsubishi.

PROTOCOL SYNOPSIS

Protocol number:	MT-8554-A02
Protocol title:	An open-label, long-term extension study of MT-8554 in postmenopausal women experiencing moderate to severe vasomotor symptoms who completed Study MT-8554-A01
Sponsor:	Mitsubishi Tanabe Pharma Development America, Inc. [name]
Development phase:	Phase II
Indication:	Treatment of moderate to severe vasomotor symptoms (VMS) associated with menopause
Investigational Medicinal Product:	MT-8554 █ mg capsules
Treatment regimen:	
 • Dose : MT-8554 5 mg* • Route : Oral • Frequency : Once daily before bedtime 
*Note: Based upon the results of Study MT-8554-A01, the dose is changed from 10 mg to 5 mg because participating subjects will no longer derive potential clinical benefit from receiving 10 mg dose. All participating subjects who reconsent to continue the study will receive MT-8554 5 mg.

Treatment duration:	Subjects will participate in the open-label period for 52 weeks
Objectives:	
Primary Objective: To assess long-term safety and tolerability of MT-8554.
 
Secondary Objectives:
 
 • To assess long-term efficacy of MT-8554 on VMS frequency and severity. • To assess long-term efficacy of MT-8554 on quality of life as measured by Menopause Specific Quality of Life (MENQOL).
Subject population:	
Naturally or surgically-induced menopausal women with moderate to severe VMS defined as follows:
 
Moderate: sensation of heat with sweating, able to continue activity
 
Severe: sensation of heat with sweating, causing cessation of activity

Planned number of subjects:	It is planned to enroll up to 364 subjects who have completed Study MT-8554-A01. The study will be finished when approximately 100 subjects complete a 52-week open-label treatment period and 30-day follow-up.

Study design:	
Study methodology:	
Study MT-8554-A02 is an open-label, long-term safety extension trial of Study MT-8554-A01. The study will be initiated during the conduct of Study MT-8554-A01.
 
Subjects who complete the preceding trial, Study MT-8554-A01, and comply with eligibility criteria for Study MT-8554-A02 will be enrolled in a 52-week open-label treatment period. Visit 7 (Week 12) of Study MT-8554-A01 will be considered Visit 1 of Study MT-8554-A02. Assessments already carried out at Visit 7 (Week 12) of Study MT-8554-A01 will not be repeated. During the 52-week open-label treatment period, subjects will attend visits every 8 weeks between Visits 1 and 3 (Weeks 12, 20, and 28) and every 12 weeks between Visits 4 and 6 (Weeks 28, 40, 52, and 64).
 
All enrolled subjects will receive MT-8554 (was 10 mg initially, switched to 5 mg*) for 52 weeks. Study drug will be administered once daily before bedtime.
 
An End of Study (EOS) Follow-up visit will be conducted by phone for safety follow-up 30 days after the end of the open-label treatment period.
 
Note: Based upon the results of Study MT-8554-A01, the dose is changed from 10 mg to 5 mg because participating subjects will no longer derive potential clinical benefit from receiving 10 mg dose. All participating subjects who reconsent to continue the study will receive MT-8554 5 mg.

Main inclusion criteria:	
 1. Signed informed consent to participate in this study. 2. Subjects who complete the preceding trial (Study MT-8554-A01) through Week 12. 3. In the Investigator's opinion, subject is able to understand the nature of the study, any risks involved in participation, and is willing to cooperate and comply with the protocol restrictions and requirements including transvaginal ultrasound and endometrial biopsy.

Main exclusion criteria:	Subjects who meet the withdrawal criteria for the preceding trial (Study MT-8554-A01).
Endpoints:	
Safety Endpoints (Primary objectives)
 
 Physical examination (including breast safety evaluation). Vital signs (blood pressure, pulse and tympanic body temperature). Electrocardiogram (ECG) parameters (including cardiac intervals: heart rate, PR, QRS, QT, QTcF and QTcB). Clinical laboratory assessments (hematology, biochemistry, coagulation and urinalysis). Reproductive hormones (luteinizing hormone [LH], follicle stimulating hormone [FSH], and estradiol [E2]). Adverse events (AEs). Endometrial safety (endometrial thickness as measured by transvaginal ultrasound, and incidence of endometrial hyperplasia as measured by endometrial biopsy). Breast safety (breast tenderness and incidence of breast cancer) Depression and anxiety as measured by 8-Item Patient Health Questionnaire (PHQ-8) and Generalized Anxiety Disorder-7 (GAD7), respectively. 
Exploratory Endpoints
 
 Frequency of VMS, which is the average daily frequency of moderate to severe VMS, defined as the sum of the number of moderate to severe VMS during 1 week divided by number of days with data. Severity of VMS, which is the average daily severity score of mild to severe VMS. Baseline VMS severity score is defined as $(2xFmo + 3xFse)/(Fmo + Fse)$, and VMS severity score for a specific week during the open label treatment period is defined as $(1xFmi + 2xFmo + 3xFse)/(Fmi + Fmo + Fse)$, where Fmi, Fmo, and Fse are the daily frequencies of mild, moderate, and severe VMS, respectively, during each applicable study week. MENQOL.
Statistical methods:	
Sample size consideration:
 
This study is an open-label extension of Study MT-8554-A01. There is no formal sample size estimation for this study. It is planned to enroll up to 364 subjects from Study MT-8554-A01.

	
The subjects who have completed Study MT-8554-A01 and comply with all eligibility criteria may be enrolled into this study.
 
Analysis Populations:
 
• Safety Population includes all subjects who received at least 1 dose of study medication.• Intent-to-treat (ITT) population includes all subjects who have at least 1 post-baseline efficacy assessment. 
Statistical Methods:
 
Where appropriate, data will be summarized descriptively (frequency and percent will be summarized for categorical variables; mean, standard deviation [SD], median, minimum, and maximum will be presented for continuous variables) by study visit and by treatment group.
 
Safety evaluation:
 
AEs are considered as treatment-emergent if they occurred after administration of the first dose of study medication or if a pre-dose event increases in severity following dosing. The frequency and incidence of treatment-emergent adverse events (TEAEs) will be summarized by System Organ Class (SOC) and Preferred Term (PT), by treatment group and overall. Summary listings will be constructed by relationship to study medication and by maximum severity. Serious TEAEs and TEAEs leading to study medication discontinuation will be provided as listings.
 
Vital signs, ECG parameters, and clinical laboratory assessments, and physical examinations will be summarized by treatment group and planned sampling point.
 
Other safety measurements (e.g., endometrial and breast safety measures, reproductive hormones, and depression [PHQ-8 and GAD7] evaluations) will be summarized in tables according to the data type. The graphs will be generated for the endpoints as needed. The data will be presented in data listings as needed. Any other safety data will be presented in tables or listings as appropriate.

--	---

LIST OF ABBREVIATIONS

Abbreviation	Definition
AE	Adverse event
CI	Confidence interval
CRO	Contract Research Organization
CS	Clinically significant
CSR	Clinical Study Report
CYP	Cytochrome P450
DDI	Drug-drug interaction
DSM-IV	Diagnostic and Statistical Manual of Mental Disorders, 4th Edition
E2	Estradiol
ECG	Electrocardiogram
eCRF	Electronic Case Report Form
EOS	End of Study
EOT	End of Treatment
FDA	Food and Drug Administration
FSH	Follicle stimulating hormone
GAD7	7-Item Generalized Anxiety Disorder questionnaire
GCP	Good Clinical Practice
HDPE	High density polyethylene

1 INTRODUCTION

MT-8554

[REDACTED] is a selective transient receptor potential melastatin 8 (TRPM8) antagonist, discovered by Mitsubishi Tanabe Pharma Corporation. Based on the compound's mechanism of action, development of MT-8554 for the treatment of vasomotor symptoms (VMS), neuropathic pain and other relevant diseases is currently under consideration.

TRPM8 is a member of the transient receptor potential cation channel family and is expressed in both C and A_δ fibers of primary afferent neurons. It is also expressed in the bladder and male genital tract. TRPM8 plays an essential role in the sensation of environmental cold¹.

MT-8554 is an orally active, potent and selective TRPM8 antagonist with a good safety profile in animals and has been shown to be safe and well tolerated in recently completed Phase I clinical studies².

It has been proposed that VMS may be triggered by small increases in core body temperature in peri- or postmenopausal women³. A decrease in intra-abdominal body temperature of around 1°C compared with that of time-matched controls was observed in rats and monkeys following administration of MT-8554². Therefore, MT-8554 may have the potential to reduce core body temperature and decrease the frequency and severity of VMS.

After menopause, up to 85% of American women have VMS, and many are affected by insomnia and sleep disturbances. Although most symptoms resolve spontaneously after about 5 years, symptoms continue in a substantial number of women^{4,5}. Hence, this study will also assess the long-term safety of MT-8554 according to the International Conference on Harmonization (ICH)-E1 guideline.

1.1 Non-clinical pharmacology

[REDACTED]

1.2 Non-clinical safety pharmacology

[REDACTED]

1.3 Non-clinical toxicology

General toxicity of MT-8554 was assessed in rats and monkeys. The approximate lethal

1.4 Clinical studies

2 STUDY OBJECTIVES AND ENDPOINTS

2.1 Study objectives

2.1.1 Primary objective

To assess long-term safety and tolerability of MT-8554.

2.1.2 Secondary objectives

- To assess long-term efficacy of MT-8554 on VMS frequency and severity.
- To assess long-term efficacy of MT-8554 on quality of life as measured by Menopause Specific Quality of Life (MENQOL).

2.2 Study endpoints

2.2.1 Safety endpoints (Primary objective)

- Physical examination (including breast safety evaluation).
- Vital signs (blood pressure, pulse and tympanic body temperature).
- Electrocardiogram (ECG) parameters (including cardiac intervals: heart rate, PR, QRS, QT, QTcF and QTcB).
- Clinical laboratory assessments (hematology, biochemistry, coagulation and urinalysis).
- Reproductive hormones (luteinizing hormone [LH], follicle stimulating hormone [FSH], and estradiol [E2]).
- Adverse events (AEs).
- Endometrial safety (endometrial thickness as measured by transvaginal ultrasound, and incidence of endometrial hyperplasia as measured by endometrial biopsy).
- Breast safety (breast tenderness and incidence of breast cancer).
- Depression and anxiety as measured by 8-Item Patient Health Questionnaire (PHQ-8) and by Generalized Anxiety Disorder-7 (GAD7), respectively.

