## **6. GENERAL CONSIDERATIONS**

### **6.1 Descriptive Statistics**

Continuous data will be summarized descriptively using the number of observations, mean, standard deviation (SD), median, minimum and maximum. Categorical data will be summarized using frequency counts and percentages. The denominator for the percentages will be the total number of subjects in the treatment group and analysis population being presented, unless otherwise specified.

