### 8.2.2 Laboratory Tests

For all continuous laboratory parameters, the lab values and change from baseline to post baseline visits are summarized by treatment group of A01 and overall and visit.

For all discrete laboratory parameters, the lab values are summarized with count and percentage by treatment group of A01 and overall and visit.

The lab tables will be generated for each Lab categories (Hematology, Biochemistry, Coagulation, Urinalysis and Hormones).

(Table 14.3.2.1, Table 14.3.2.2, Table 14.3.2.3, Table 14.3.2.4, Table 14.3.2.5)

All laboratory data will be listed with clinically relevant values flagged (L=Lower than lower limit of normal range or H=Higher than upper limit of normal range).

In addition, following clinical relevant ranges (and flags) will also be considered for summary table. The count and percent of subjects meeting the criteria will be presented. (Table 14.3.2.6)

- ALT  $\geq 3 \times$  Upper Limit of Normal Range (ULN), 5 $\times$  ULN, 8 $\times$  ULN, 10 $\times$  ULN
- AST and/or ALT  $\geq 3 \times$  ULN, 5 $\times$  ULN, 8 $\times$  ULN, 10 $\times$  ULN
- AST and/or ALT  $\geq 3 \times$  ULN with Total bilirubin  $\geq 2 \times$  ULN
- Total bilirubin  $\geq 2 \times$  ULN
- Creatinine  $\geq 2 \times$  ULN

The all clinical lab tests will be listed.

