**Table 6 Routine Laboratory Tests**

Hematology:	
Hemoglobin	Mean corpuscular hemoglobin
Hematocrit	Mean corpuscular hemoglobin concentration
Platelet count	Mean corpuscular volume
Red blood cell count	White blood cell count and differential
Biochemistry:	
Alkaline phosphatase	Cholesterol
Aspartate aminotransferase	Triglycerides
Alanine aminotransferase	High density lipoprotein-cholesterol
Gamma-glutamyl transpeptidase	Low density lipoprotein-cholesterol
Potassium	Protein (total)
Sodium	Albumin
Chloride	Creatine kinase
Inorganic phosphate	Creatinine
Glucose	
Urea	
Bilirubin (direct and total)	
Coagulation:	
Prothrombin time	Activated partial thromboplastin time
International normalized ratio	
Urinalysis:	
Specific gravity, pH, protein, glucose, ketones, urobilinogen, blood	
Microscopic examination 	
Reproductive hormones	
Luteinizing hormone (LH)	
Follicle stimulating hormone (FSH)	
Estradiol (E2)	

 Performed only if required, based on urinalysis results.

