## 8.5 Exploratory Analysis Excluding Some Study Sites

During the MT-8554-A01, the Sponsor observed a significant degree of study drug non-compliance at a few study sites, where some of these were clustered geographically and had study subjects duplication.

The Sponsor also observed 8 study sites (site number 104, 108, 112, 114, 119, 128, 144, and 158) with significant IP non-compliance based on MT-8554 PK levels. Among them, 4 sites (site number 104, 112, 114, and 119) had highest number of IP non-compliance based on PK levels, were among the high enrollers (site number 112 and 114 were top enrollers and 104 and 119 were among the top 8 enrollers), and were located at a close proximity to each other in the South Florida. The Sponsor initiated a comprehensive re-review to verify the operational conduct of the study.

The Sponsor's review team concluded that at these 4 Florida sites, training and monitoring was conducted similar to all other sites as per standards, and no concerns were identified by the study monitors during the conduct of the study. The Sponsor considered the possibility that the subjects' poor IP compliance could be due to early onset adverse events which might have prevented them from continuation of MT-8554. However, it was noted that there was a lack of adverse events reporting from these 4 Florida sites in comparison to the all others sites. The incidences of AEs at these 4 sites were 31.8, 37.0, 31.6 and 4.3% as compared to 44.1, 39.7, 49.3 and 64.3% at the other sites in placebo, 1, 5, and 10 mg groups respectively, in MT-8554-A01.

Of these 4 sites, one site was identified a duplicate subject during the screening period, which was dropped out of the study. The Sponsor conducted an additional database search to exclude unidentified duplicate subjects. The Sponsor identified 12 subjects at these 4 Florida sites, which were suspected of being duplicates based on date of birth, height, weight medical history, and medications. Later, all these 12 subjects were confirmed by the quality assurance review of the sites as being duplicates, at least one subject at each site.

Therefore, it was considered to conduct the statistical analyses without the data from these sites. As the exploratory analyses, the main efficacy and safety analyses specified as following list will be performed with the ITT and safety population excluding the 4 sites subjects.

No.	Title of Table	Analysis Population

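### For 27 of the 31 numeric hematology, biochemistry and coagulation rows, SAP 8.2.2 plans no threshold count and no shift table, although laboratory safety is a primary endpoint

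*Protocol*

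**What the plan says.** Protocol 2.2.1 places "Clinical laboratory assessments (hematology, biochemistry, coagulation and urinalysis" under the primary objective, and SAP 2.2.1 repeats this. Protocol Table 1 schedules routine laboratory tests at Visits 1 to 6.

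SAP 8.2.2 sets the analysis. For continuous parameters, "the lab values and change from baseline to post baseline visits are summarized by treatment group of A01 and overall and visit". SAP 6.1 says what such a summary contains: "Continuous data will be summarized descriptively using the number of observations, mean, standard deviation (SD), median, minimum and maximum". Discrete parameters get counts and percentages by visit.

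Table 14.3.2.6 adds subject counts for ALT, for AST and/or ALT (alone and with raised total bilirubin), for total bilirubin, and for creatinine. For everything else the low/high information goes to a listing: "All laboratory data will be listed with clinically relevant values flagged".

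Two other rules matter:

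- SAP 7.2 keeps unscheduled visits and retests out of by-visit summary tables. Where several visits fall in one window, it uses the one closest to the nominal day.
- Protocol 6.5.7 and 8.5.1 make abnormalities that the investigator judges clinically significant reportable as adverse events. SAP 8.2.1 counts treatment-emergent events by System Organ Class and Preferred Term.

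**The concern.** The trial has no concurrent control and its main question is long-term safety. A rare laboratory effect typically shows as a few women with large changes, not as a move in the group average. The table that finds it counts women by baseline category and worst category on treatment.

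The SAP uses that format elsewhere. QTc has threshold counts and shift tables (8.2.4), endometrial histology has a shift table (8.2.7.2), and endometrial thickness has categories of change (8.2.7.1). Most laboratory analytes have nothing equivalent. A reader of the study report could not find, in any laboratory table, how many women became newly low in platelets or newly high in potassium or creatine kinase. That reader would have to reconstruct it from the listings.

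**Working it through.** The plan states no sample size calculation, margin or error rate, so it has no figure of its own to reproduce. The check is a count of rows, then a look at what the planned statistics can show.

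**1. Row count (SAP Table 6 against the Table 14.3.2.6 criteria)**

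- Hematology: 8 rows, with "White blood cell count and differential" taken as one.
- Biochemistry: 20, with direct and total bilirubin taken separately.
- Coagulation: 3.
- Total: 8 + 20 + 3 = 31. With a threshold count: ALT, AST, total bilirubin, creatinine = 4. Without: 31 − 4 = 27.

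The denominator depends on convention:

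| Convention | Numeric rows | Without a count |
|---|---|---|
| As above | 31 | 27 |
| Bilirubin as one row | 30 | 26 |
| Adding specific gravity and pH | 33 | 29 |
| Adding LH, FSH, estradiol | 34 | 30 |
| Differential as 5 extra rows (assumed) | 36 | 32 |
| Adding all of these (bilirubin separate) | 41 | 37 |

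In every version exactly 4 have a count.

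**2. What the mean shows.** If k of n women shift by s standard deviations, the mean moves by k × s / n SD, against a standard error of about 1/√n. Take k = 3 and s = 3 to 5 (assumed). The values of n are the protocol's approximately 100 completers and its enrolment ceiling of 364.

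- n = 100: 9/100 to 15/100 = 0.09 to 0.15 SD; standard error 0.10.
- n = 364: 9/364 to 15/364 = 0.025 to 0.041 SD; standard error 0.052.

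The mean moves by at most 1.5 standard errors, so it would hardly show these women.

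**3. What the minimum and SD add.** Assume 200 women whose platelet change has mean 0 and SD 35 (×10⁹/L), with k of them falling by 160. The variance is (1 − k/n) × 35² + (k/n) × 160² − mean².

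- k = 4: mean −640/200 = −3.2; SD √(1200.5 + 512 − 10.24) = 41.3; minimum about −160.
- k = 1: mean −160/200 = −0.8; SD √(1218.9 + 128 − 0.64) = 36.7; minimum about −160.

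The minimum stands out: 196 unaffected women would give an expected minimum of about −96. It therefore signals that something happened. It is the same for one woman as for four, and it does not show whether the low value was already present at baseline. A shift table would show 4/200 = 2.0% (exact 95% CI 0.5% to 5.0%).

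**4. Which values reach the by-visit tables.** Protocol 6.5.7 requires abnormal tests to be repeated. Under SAP 7.2 the scheduled value stays in the table, but a worse retest, or an abnormality first seen at an unscheduled visit, does not enter. An early-termination visit late in the Week 40 window (Days 240 to 323) gives way to an on-time visit at Day 281. Table 3 has no post-baseline window before Day 113, so an early-termination draw before then belongs to no analysis visit.

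**5. Would there be cases to count?** At an assumed true rate of 1% to 3%, the chance of at least one case in 100 women, 1 − (1 − p)^100, is 63.4% to 95.2%. The chance of at least two is 26.4% to 80.5%. Small counts are the likely outcome, and these are what a count table shows and a mean does not.

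**The case against.** The best defence is that nothing is lost. SAP 6.1 gives the median, minimum and maximum as well as the mean, for values and for changes. Every result is listed with flags, in subject and visit order and including unscheduled and retest values, so whether an abnormality is new can be read for each woman. The investigator must classify all laboratory data, and what is judged clinically significant enters the adverse event counts. Marked abnormalities are the ones most likely to be judged so. The protocol promises only tables suited to the data type, and no test or decision rule depends on the result.

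Much of this stands, and it rules out two stronger readings. A reader might infer that these analytes get only means; SAP 6.1 says otherwise. A reader might also infer that an affected woman would be counted nowhere; the adverse event route contradicts that. What remains is narrower. An extreme is not a number of women, a listing is not a table, and an abnormality that the investigator does not call clinically significant is in no planned count for these 27 rows.

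It is also tempting to say that adverse event reporting cannot be relied on, because SAP 8.5 reports that "it was noted that there was a lack of adverse events reporting from these 4 Florida sites". The documents do not carry that argument here. The incidences are from A01, at sites with poor drug compliance on PK levels, where laboratory values would show little drug effect either. The gaps are uneven (31.8 against 44.1% on placebo, 37.0 against 39.7% on 1 mg, 31.6 against 49.3% on 5 mg, 4.3 against 64.3% on 10 mg). The section does not look at laboratory events, and the SAP already repeats the main adverse event tables without those sites. The point does not rest on it.

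**Conclusion.** The point holds in limited form. For 27 of 31 numeric rows (differential as one row, urinalysis and hormones left out), a primary safety endpoint has no planned threshold count or shift table. No laboratory table will state how many women became newly abnormal on these analytes. The restriction of by-visit tables to one scheduled value per window means that even the minimum and maximum can miss a woman's worst result.

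The row count rests on the documents and the stated convention. The dilution and platelet figures rest on assumed shifts, SDs and case numbers and only illustrate the mechanism. The data will be collected and listed in any case, so this is a gap in tabulation, not in data. It is a cheap improvement and not a flaw that threatens the study's conclusions.

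**What to change.** In SAP 8.2.2, for every Table 6 analyte with a reference range, add a low/normal/high shift table from A02 baseline to the lowest, and separately to the highest, post-baseline value per woman. Present it by A01 treatment group and overall. Say explicitly that unscheduled and retest values are included, because SAP 7.2 otherwise excludes them from by-visit tables. Take as denominator the women with a baseline and at least one post-baseline value.

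In Table 14.3.2.6, show separately the women who did not already meet the criterion at baseline.

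This needs SAP wording and a standard table shell. The low/high flags are already required for the listing, and no new data are collected. The cost is more table pages, and some isolated out-of-range values without clinical meaning will be counted.
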